## 13.0 DATA AND SAFETY MONITORING PLAN

### 13.1 Overall Scope of Monitoring Activities

Institutional support of trial monitoring will be in accordance with the FRED HUTCH/University of Washington Cancer Consortium Institutional Data and Safety Monitoring Plan (DSMP). Under the provisions of this plan, FRED HUTCH Clinical Research Support coordinates data and compliance monitoring conducted by consultants, contract research organizations, or FRED HUTCH employees unaffiliated with the conduct of the study. Independent monitoring visits occur at specified intervals determined by the assessed risk level of the study and the findings of previous visits per the institutional DSMP.

A Steering Committee, comprising the PI and/or designee, the IMTX medical director and study biostatistician, will act in an advisory capacity to the PI throughout the trial, as needed. If a stopping rule is triggered, further enrollment will be suspended pending review by the Steering Committee.

In addition, protocols are reviewed at least annually and as needed by the Consortium Data and Safety Monitoring Committee (DSMC), FRED HUTCH Scientific Review Committee (SRC) and the FRED HUTCH/University of Washington Cancer Consortium Institutional Review Board (IRB). The review committees evaluate accrual, adverse events, stopping rules, and adherence to the applicable data and safety monitoring plan for studies actively enrolling or treating subjects. The IRB reviews the study progress and safety information to assess continued acceptability of the risk-benefit ratio for human subjects. Approval of committees as applicable is necessary to continue the study.

The trial will comply with the standard guidelines set forth by these regulatory committees and other institutional, state and federal guidelines. The conduct of this trial will be further monitored by the IIRC Data and Safety Monitoring Board (DSMB) in accordance with an approved DSMB Charter.

### **13.2 Monitoring the Progress of Trial and Safety of Participants**

The first level of trial oversight for this protocol will be provided by the Principal Investigator, the Research Nurse, and Research Coordinator(s), who will provide continuous oversight of the trial. These individuals will meet at least monthly to review recently acquired data, stopping rules, and adverse events. Serious adverse events will be reviewed upon occurrence to ensure prompt and accurate reporting to the Institutional Review Board (IRB). The data recorded in the research charts and protocol database will be compared with the actual data available from the medical record and/or clinical histories. Data detailed in the research case report forms (CRFs) will include the nature and severity of all toxicities. The Principal Investigator and all other investigators on the protocol have received formal training in the ethical conduct of human research.

## **14.0 DATA MANAGEMENT/CONFIDENTIALITY**

The medical record containing information regarding treatment of the patient will be maintained as a confidential document, within the guidelines of the Fred Hutchinson Cancer Center and the University of Washington Medical Center.

The investigator will ensure that data collected conform to all established guidelines for coding collection, key entry and verification. Each subject is assigned a unique subject number to assure subject confidentiality. Information forwarded to the FDA, NIH, NCI or other agencies about subjects on this protocol refers to subjects by a coded identifier and not by name. Subjects will not be referred to by this number, by name, or by any other individual identifier in any publication or external presentation. The licensed medical records department, affiliated with the institution where the subject receives medical care, maintains all original inpatient and outpatient chart documents.

The research team will maintain Case Report Forms (CRFs) and associated research documentation for each patient treated under the protocol. This documentation includes both clinical data and study-specific documents for each patient. The Principal Investigator or a designee will verify completed CRFs against source documentation on an ongoing basis as they are completed for individual subjects. Data required for analysis of subjects treated on this protocol will be maintained in a password-protected study-specific database. Data from the CRFs are keyed directly into the database by authorized research staff and verified on an ongoing basis.

## **15.0 TERMINATION OF STUDY**

The study will terminate after the last treated patient has completed 90 days of follow-up following liso-cel infusion. CRS and ICANS will be evaluated until day 28 post liso-cel treatment. Disease restaging should be performed approximately on day 28 and day 90. Day-90 disease restaging may be performed

by the patient's local oncologist. The study team will contact the local oncologist office by a letter/phone call to request the results of the day-90 restaging, if completed as per standard-of-care.

The PI may terminate the study at any time. The IRB and FDA also have the authority to terminate the study should it be deemed necessary.

**APPENDIX A: ASTCT Cytokine Release Syndrome (CRS) Consensus Grading**

CRS Parameter	Grade 1	Grade 2	Grade 3	Grade 4
Fever 	Temperature $\geq 38^{\circ}\text{C}$	Temperature $\geq 38^{\circ}\text{C}$	Temperature $\geq 38^{\circ}\text{C}$	Temperature $\geq 38^{\circ}\text{C}$
With				
Hypotension	None	Not requiring vasopressors	Requiring a vasopressor with or without vasopressin	Requiring multiple vasopressors (excluding vasopressin)
And/or 				
Hypoxia	None	Requiring low-flow nasal cannula  or blow-by	Requiring high-flow nasal cannula  , facemask, nonrebreather mask, or Venturi mask	Requiring positive pressure (e.g., CPAP, BiPAP, intubation and mechanical ventilation)

Organ toxicities associated with CRS may be graded according to CTCAE v5.0 but they do not influence CRS grading.

 Fever is defined as temperature  $\geq 38^{\circ}\text{C}$  not attributable to any other cause. In patients who have CRS then receive antipyretic or anticytokine therapy such as tocilizumab or steroids, fever is no longer required to grade subsequent CRS severity. In this case, CRS grading is driven by hypotension and/or hypoxia.

 CRS grade is determined by the more severe event: hypotension or hypoxia not attributable to any other cause. For example, a patient with temperature of  $39.5^{\circ}\text{C}$ , hypotension requiring 1 vasopressor, and hypoxia requiring low-flow nasal cannula is classified as grade 3 CRS.

 Low-flow nasal cannula is defined as oxygen delivered at  $\leq 6\text{L}/\text{minute}$ . Low flow also includes blow-by oxygen delivery, sometimes used in pediatrics. High-flow nasal cannula is defined as oxygen delivered at  $>6\text{L}/\text{minute}$ .

**APPENDIX B. 2014 NIH CRS Grading (“Lee criteria”)**

Grade	Toxicity
Grade 1	Symptoms are not life threatening and require symptomatic treatment only, e.g., fever, nausea, fatigue, headache, myalgias, malaise
Grade 2	Symptoms require and respond to moderate intervention Oxygen requirement <40% or Hypotension responsive to fluids or low dose of one vasopressor or Grade 2 organ toxicity per CTCAE 4.0
Grade 3	Symptoms require and respond to aggressive intervention Oxygen requirement $\geq 40\%$ or Hypotension requiring high dose or multiple vasopressors or Grade 3 organ toxicity or grade 4 transaminitis
Grade 4	Life-threatening symptoms Requirement for ventilator support or Grade 4 organ toxicity (excluding transaminitis)
Grade 5	Death

Criteria defining high-dose vasopressor use	
Vasopressor	Dose
Norepinephrine monotherapy	$\geq 20 \mu\text{g}/\text{min}$
Dopamine monotherapy	$\geq 10 \mu\text{g}/\text{min}$
Phenylephrine monotherapy	$\geq 200 \mu\text{g}/\text{min}$
Epinephrine monotherapy	$\geq 10 \mu\text{g}/\text{min}$
If on vasopressin	Vasopressin + norepinephrine equivalent of $\geq 10 \mu\text{g}/\text{min}^*$
If on combination vasopressors (not vasopressin)	Norepinephrine equivalent of $\geq 20 \mu\text{g}/\text{min}$

\*VASST Trial vasopressor equivalent equation: norepinephrine equivalent dose = [norepinephrine ( $\mu\text{g}/\text{min}$ )] + [dopamine ( $\mu\text{g}/\text{kg}/\text{min}$ ) 2] + [epinephrine ( $\mu\text{g}/\text{min}$ )] + [phenylephrine ( $\mu\text{g}/\text{min}$ ) 10].

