**Table 1. CRS and ICANS after CD19 CAR T-cell therapy for R/R LBCL**

	Axi-cel			Brexu-cel	Tisa-cel	Liso-cel
	ZUMA-1 	Nastoupil et al 	Jacobson et al 	ZUMA-2 	JULIET 	TRANSCEND 
No. of patients treated	101	275	122	60	93	269
CRS (graded according to the 2014 Lee criteria for all studies except JULIET*)						
Any grade / ≥ grade 3	93 % / 11%	91% / 7%	93% / 16%	91%/15%	58%/22%	42%/2%
Median time to onset, range	2 days (1-12)	NR	3 days (0-20)	3 days (1-13)	3 days (3-9)	5 days (1-14)
Median duration, range	8 days (NR)	NR	6 days (1-27)	10 days (1-50)	7 days (2-30)	NR
ICANS (graded according to the CTCAE 4.03)						
Any grades / ≥ grade 3	64 % / 28%	69% / 31%	70% / 35%	63%/31%	21%/12%	30%/10%
Median time to onset, range	5 days (1-17)	NR	5 days (0-34)	6 days (1-32)	6 days (1-17)	9 days (1-66)
Median duration, range	17 days (NR)	NR	7 days (1-52)	21 days (2-454)	14 (NR)	NR

Abbreviations: Axi-cel, axicabtagene ciloleucel; brexu-cel, brexucabtagene autoleucel; tisa-cel, tisagenlecleucel; liso-cel, lisocabtagene maraleucel; CRS, cytokine release syndrome; ICANS, immune effector cell-associated neurotoxicity syndrome; NR, not reported. \*CRS graded using the PENN scale.

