### 3.5 Secondary Endpoints

- Peak CRS grade according to the 2019 American Society for Transplantation and Cellular Therapy (ASTCT) consensus criteria within 28 days after liso-cel infusion. CRS will also be graded according to the 2014 NIH criteria to allow comparisons to historical controls.
- Peak ICANS grade according to the 2019 ASTCT consensus criteria within 28 days after liso-cel infusion. ICANS will also be graded according to the NCI CTCAE Version 5.0 to allow comparisons to historical controls.
- Rate and duration of hospitalization after liso-cel treatment.
- Cumulative corticosteroids dose within 28 days after liso-cel infusion.
- Adverse events (AEs) according to the NCI CTCAE Version 5.0 within the first 28 days after liso-cel administration.
- Disease response to CAR T-cell therapy approximately 28 days and 90 days after CAR T-cell infusion according to the Lugano criteria.

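### Appendix B prints the high-dose dopamine cut per minute although its own equation uses dopamine per kg per minute; taken literally, some dopamine-only patients would be Lee grade 3 instead of grade 2

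*Combined protocol and SAP*

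**What the plan says.** Section 3.5 makes peak CRS grade a secondary endpoint on the ASTCT scale and adds a second grading: "CRS will also be graded according to the 2014 NIH criteria". The stated purpose there, and again in Section 11.3, is comparison with historical controls. Section 11.3 points to Appendix B for that second scale.

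In Appendix B, vasopressor dose separates Lee grade 2 from grade 3:

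- Grade 2 includes "Hypotension responsive to fluids or low dose of one vasopressor".
- Grade 3 includes "Hypotension requiring high dose or multiple vasopressors".

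What counts as a high dose is set by the sub-table headed "Criteria defining high-dose vasopressor use", the only such definition in the documents. Its dopamine row is "Dopamine monotherapy $\geq 10 \mu\text{g}/\text{min". The other single-drug rows are also per minute: norepinephrine 20, phenylephrine 200 and epinephrine 10 micrograms/min. The vasopressin row, "Vasopressin + norepinephrine equivalent of" 10 micrograms/min or more, carries an asterisk to a footnote that begins "VASST Trial vasopressor equivalent equation: norepinephrine equivalent dose". That footnote enters dopamine in micrograms/kg/min and the other three drugs in micrograms/min.

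Table 1 in Section 1.2 gives the historical CRS rates, "graded according to the 2014 Lee criteria for all studies except JULIET". For liso-cel they are 42% for any grade and 2% for grade 3 or higher.

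**The concern.** One appendix uses two units for the same drug. The equation scales dopamine by body weight and the single-drug row does not, yet the number 10 in that row sits beside cuts for other drugs that are meant to mark a comparable intensity of support. If the row is short of a per-kg term, a grader who follows the appendix would classify almost any dopamine infusion as high dose.

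The Lee grade is collected so that this trial can be set beside a liso-cel reference with a grade 3 or higher rate of 2%. Against so low a figure, in a study of at most 25 patients, a single misgraded patient would be visible.

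**Working it through.** **Inputs.** From Appendix B: the single-drug cuts (norepinephrine 20, dopamine 10, phenylephrine 200, epinephrine 10, all in micrograms/min); the vasopressin-row requirement of at least 10 micrograms/min norepinephrine equivalent; and the equation, with factor 2 for dopamine and factor 10 for phenylephrine. Body weight is not in the documents, so 50 to 120 kg is assumed. The operators before 2 and 10 are missing from the text as read from the PDF, so both possibilities are shown for dopamine. For phenylephrine, division is assumed, because multiplication would give 200 × 10 = 2,000. The plan states the dopamine cut without a derivation, so there is no calculation to reproduce first.

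**Step 1: printed cut per kg.** Printed cut ÷ weight:

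- 50 kg: 10/50 = 0.20 micrograms/kg/min
- 70 kg: 10/70 = 0.14
- 120 kg: 10/120 = 0.08

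**Step 2: compare with the other rows in norepinephrine equivalents.** The other rows are norepinephrine 20, epinephrine 10 and phenylephrine 200/10 = 20, so the lowest is 10.

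| Weight | Dopamine cut, ÷2 | Gap to 10 | Dopamine cut, ×2 | Gap to 10 |
|---|---|---|---|---|
| 50 kg | 0.100 | 100-fold | 0.400 | 25-fold |
| 70 kg | 0.071 | 140-fold | 0.286 | 35-fold |
| 120 kg | 0.042 | 240-fold | 0.167 | 60-fold |

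Under either operator, the printed row is 25- to 240-fold below the lowest other row.

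**Step 3: compare with the vasopressin row.** Dopamine needed for an equivalent of 10:

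- Division: 10 × 2 = 20 micrograms/kg/min, or 1,000 to 2,400 micrograms/min at 50 to 120 kg.
- Multiplication: 10/2 = 5 micrograms/kg/min, or 250 to 600 micrograms/min.

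Against a stand-alone cut of 10 micrograms/min, adding vasopressin would raise the dopamine cut 100- to 240-fold (division) or 25- to 60-fold (multiplication). For the other drugs it lowers or keeps the cut: norepinephrine 10/20 = 0.5, epinephrine 10/10 = 1, phenylephrine 100/200 = 0.5. This is a check of coherence only. On a plain reading, a patient on two vasopressors is already Lee grade 3.

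**Step 4: try 10 micrograms/kg/min.** The norepinephrine equivalent is 10/2 = 5 (division) or 10 × 2 = 20 (multiplication). The ratio of the with-vasopressin cut to the stand-alone cut is 20/10 = 2 or 5/10 = 0.5. Both results are of the same order as the other rows. Only multiplication matches the 20 for norepinephrine. In absolute terms the cut becomes 500 to 1,200 micrograms/min.

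**Step 5: which doses change grade.** For dopamine alone with no other grade 3 feature:

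- Below 10 micrograms/min (0.20 micrograms/kg/min at 50 kg, 0.08 at 120 kg): grade 2 on both readings.
- From there to just under 10 micrograms/kg/min: grade 3 as printed, grade 2 with the per-kg cut.
- At 10 micrograms/kg/min or more: grade 3 on both readings.

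**Step 6: effect of one patient (hypothetical).** 1/25 = 4 percentage points of all patients; 1/10 = 10 points of the IV expansion cohort.

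**The case against.** **The correct value is not proved.** A reader might infer that the documents establish 10 micrograms/kg/min. They do not. The cited 2014 criteria (reference 46) are not reproduced beyond Appendix B. If the missing operator is division for dopamine, as seems natural for phenylephrine, 10 micrograms/kg/min is worth only 5 norepinephrine equivalents. Adding vasopressin would then double the dopamine cut where it halves or keeps the others. This objection stands: the mismatch and the implausibility of the printed unit are shown, and the replacement value is presumed.

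**Different units need not conflict.** The equation is tied to the vasopressin row and is not applied to the single-drug rows. That is true, and the case therefore rests on plausibility. But a 25- to 240-fold gap, under either operator and at any weight in the assumed range, is hard to read as deliberate.

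**The text may be damaged.** Operators are missing from the same footnote, so a lost per-kg term cannot be excluded. It is unlikely, because the per-kg term survives in the equation a few lines below, but the PDF has to be checked.

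**Graders have the published scale.** Section 3.5 names the 2014 criteria without the appendix. Section 11.3, however, cites both, so Appendix B is an operative grading rule.

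**The effect is small.** A reader might infer that the efficacy conclusion or patient management is at risk. The documents do not support that:

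- The primary endpoint is absence of any grade CRS, so a move between grades 2 and 3 leaves it and the BOP2 boundaries alone.
- The stopping rules in Section 12.4 use deaths and disease response.
- ASTCT grading in Appendix A has no dose cut; CRS hypotension needing any vasopressor is at least grade 3.
- Up-titration in Section 6.1 starts when CRS or ICANS develops, whatever the Lee grade.
- Section 12.3 plans descriptive statistics, with no test on Lee grade and no separate analysis of the IV cohort.

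Section 2.3.2 also reports one patient with CRS of grade 3 or higher among the first 15. If that count is ASTCT-graded, which the section does not say, at most one of those patients received a vasopressor for CRS. All of this stands and limits the point.

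**Conclusion.** The point holds as a unit error in an operative grading table, and its consequence is minor. The printed cut for dopamine alone is almost certainly missing its per-kg term: at an assumed 50 to 120 kg it equals 0.08 to 0.20 micrograms/kg/min, or 0.04 to 0.40 norepinephrine equivalents, against 10 to 20 in the other single-drug rows. No other section settles the unit.

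A reader might also infer that every dopamine-only patient below 10 micrograms/kg/min changes grade. The shift has a floor at 10 micrograms/min, applies only without another grade 3 feature, and has its upper limit at 10 micrograms/kg/min only if that is the intended cut.

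The consequence is confined to the secondary Lee peak CRS grade and its comparison with the historical 2%. The documents report no dopamine use, so the number affected may be zero. Any error from the literal reading would raise the grade and so count against anakinra.

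**What to change.** 1. Confirm that the PDF prints the dopamine row without a per-kg term.
2. Verify the unit and value against the cited 2014 criteria (reference 46), and correct the row to the per-kg unit, presumably 10 micrograms/kg/min or more.
3. Re-check the Lee grade of any treated patient who received dopamine alone. Section 11.3 already requires CRS-related interventions to be recorded, so these patients can be found.

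The cost is one corrected appendix line and a review of the charts, if any, that show dopamine as the only vasopressor. Design, sample size and conduct stay as they are.

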## APPENDIX C: ASTCT ICANS\* Consensus Grading

\* Immune Effector Cells (IEC)-associated neurotoxicity syndrome (ICANS)

Neurotoxicity Domain	Grade 1	Grade 2	Grade 3	Grade 4
ICE score 	7-9	3-6	0-2	0 (patient is unarousable and unable to perform ICE)
Depressed level of consciousness 	Awakens spontaneously	Awakens to voice	Awakens only to tactile stimulus	Patient is unarousable or requires vigorous or repetitive tactile stimuli to arouse. Stupor or coma
Seizure	N/A	N/A	Any clinical seizure focal or generalized that resolves rapidly or nonconvulsive seizures on EEG that resolve with intervention	Life-threatening prolonged seizure (>5 min); or Repetitive clinical or electrical seizures without return to baseline in between
Motor findings 	N/A	N/A	N/A	Deep focal motor weakness such as hemiparesis or paraparesis
Elevated ICP/cerebral edema	N/A	N/A	Focal/local edema on neuroimaging 	Diffuse cerebral edema on neuroimaging; decerebrate or decorticate posturing; or cranial nerve VI palsy; or papilledema; or Cushing's triad

ICANS grade is determined by the most severe event (ICE score, level of consciousness, seizure, motor findings, raised ICP/cerebral edema) not attributable to any other cause; for example, a patient with an ICE score of 3 who has a generalized seizure is classified as grade 3 ICANS.

N/A indicates not applicable.

 ICE Score:

- **Orientation:** orientation to year, month, city, hospital; 4 points
- **Naming:** ability to name 3 objects (e.g. point to clock, pen, button): 3 points
- **Following commands:** ability to follow simple commands (e.g., “show me 2 fingers” or “close your eyes and stick out your tongue”): 1 point
- **Writing:** ability to write a standard sentence (e.g. “Our national bird is the bald eagle”): 1 point
- **Attention:** ability to count backwards from 100 by 10: 1 point

 A patient with an ICE score of 0 may be classified as grade 3 ICANS if awake with global aphasia, but a patient with an ICE score of 0 may be classified as grade 4 ICANS if unarousable.

 Depressed level of consciousness should be attributable to no other cause (e.g., no sedating medication).

 Tremors and myoclonus associated with immune effector cell therapies may be graded according to CTCAE v5.0, but they do not influence ICANS grading.

 Intracranial hemorrhage with or without associated edema is not considered a neurotoxicity feature and is excluded from ICANS grading. It may be graded according to CTCAE v5.0.

**APPENDIX D: Schedule of Assessments**

Assessment	Pre-Lymphodepletion Evaluations	Day of liso-cel Infusion (Day 0)	Follow-up Evaluations										Comments
			1	3	7	10	13	14	21	28	90		
I/E criteria	X												
Medical history	X	X	X	X			X	X	X				
Physical exam	X	X	X	X			X	X	X				
ICE score		X	X	X	X	X		X	X	X			
Height/weight	X												
Karnofsky performance status	X												
CRS/ICANS-related interventions			Continuous recording from day 0-28										
AEs			Continuous recording from day 0-28										
Vitals including pulse oximetry	X		Prior to and 30 minutes after anakinra administration on days 0 through 13										For patients receiving step-up dosing, vital signs will be obtained every 4 hours per standard-of-care.
Chest x-ray	X												
12-lead ECG	X												
MUGA/ECHO	X												
CT/PET or CT	X									X	X	As clinically indicated	
BMA and biopsy	X									X	X	As clinically indicated	
Lumbar puncture	X									X	X	As clinically indicated	
Lymphodepleting chemotherapy												Lymphodepleting chemotherapy per	

Assessment	Pre-Lymphodepletion Evaluations	Day of liso-cel Infusion (Day 0)	Follow-up Evaluations									Comments
			1	3	7	10	13	14	21	28	90	
												institutional practice
Liso-cel administration		X										liso-cel infusion per institutional practice
Anakinra administration			day 0-13									
Laboratory evaluations												
Pregnancy test	X											
CBC, differential	X	X	X	X	X	X		X	X	X		
Renal/Hepatic Function Panel	X	X	X	X	X	X		X	X	X		
Uric acid	X	X	X	X	X	X		X	X	X		
Serum ferritin	X	X	X	X	X	X		X	X	X		
CRP	X	X	X	X	X	X		X	X	X		
IL-6	X	X	X	X	X	X		X	X	X		
PT, PTT, fibrinogen, thrombin time and D-dimer	X	X	X	X	X	X		X	X	X		
Quantitative serum IgG level	X											
Triglycerides	X	X	X	X	X	X		X	X	X		
PK samples		X 	X 									

Approximately 4 hours after the end of the first anakinra administration

Approximately 24 hours (+/- 1 hour) after the end of the first anakinra administration and prior to the second anakinra administration

The proposed days of all assessments and laboratory evaluations are approximate and may vary due to scheduling, clinical factors, research priorities or other considerations. All timepoints may not be collected. Laboratory research evaluations may vary according to clinical and research priorities.
